8.4 Definition of End of Study

The end of trial visit will be the last subject last visit which will occur at the follow up visit, two days after the MRE examination, or in case of an ongoing AE at the follow up visit, any additional visit required for AE follow-up.

8.5 Medical Care of Subjects after End of Study

The trial will only include healthy volunteers and there is therefore not need for medical care after the trial. However, in case the MRE examination reveals any relevant previously unknown medical condition, the subject will be informed and guided to contact appropriate medical expertise.

8.6 Planned Sample Size and Number of Trial Centres

It is planned to enrol 10 evaluable subjects in a single clinical site.

9 INVESTIGATIONAL PRODUCT AND PROCEDURES

9.1 Investigational product

Lumentin® 44 Powder for oral foam (Table 1) will be manufactured by Apotek Production & Laboratories AB, [name], Sweden and provided in labelled white sachets containing 17.4 g powder. Potable water (commercially available still water 0.5 L per bottle) for the preparation of the foam will be used.

Table 1: Lumentin® 44 Powder for oral foam

Ingredients	Concentration (g/sachet)
Egg White Powder	10.0
Sodium dihydrogen phosphate dihydrate (NaH ₂ PO ₄ • 2H ₂ O) ¹	1.0
Dipotassium phosphate (K ₂ HPO ₄) ¹	3.4
Xanthan gum ¹	2.5
Flavour ²	0.5

1) Ph. Eur.: European Pharmacopeia

2) The flavour complies with the regulations (EC) 1334/2008 and (EC) 178/2002 concerning flavouring in food and food additives.

Lumentin® 44 powder for oral foam will be delivered from APL to the clinical site, by order via the hospital pharmacy and stored temporarily at the site. The investigational product (Lumentin® 44 foam) is then prepared in-situ by adding 0.5 L potable water to Lumentin® 44 powder contained in one sachet, and the blend is then mixed to a stable foam in a dedicated preparation unit. The freshly prepared foam will be administered to the patient within 5 to 10 minutes as directed in the clinical trial protocol. The in-situ preparation will follow a procedure attached to the clinical trial protocol. The staff responsible for the in-situ preparation will be trained using the procedure and their training documented in the Trial Master File (TMF). Two sachets (0.9 L foam per sachet) will be required per subject.

For a detailed description of the preparation of Lumentin® 44 Foam (see Appendix 1 Lumentin® 44 : Lumentin 44 reconstitution protocol summary).

Lumentin® 44 Foam contains the same ingredients as Lumentin® 44 Powder for oral foam, see [Fel! Hittar inte referenskälla.](#), except for water added during the preparation.

9.2 Dosage and Administration

The Investigational products will be taken orally by the subject during a period of 30 minutes - 1 hour.

A volume of 1.1 L to 1.5 L shall be consumed. A steady intake rate of the contrast agent is recommended to guarantee fullness of the gastrointestinal tract from stomach to terminal ileum of the small bowel.

The intake of the contrast agent will be stopped in case of an AE occurs or if the subject is unable to consume more than 1.1 L within 1 and ½ hour. The subject will be withdrawn in case the intake of the contrast agent has to be stopped.

The subject will be withdrawn from the trial if the maximum volume of the Investigational product taken by the subject is less than 1.1 L.

There is no risk of overdose.

9.3 Packaging, Labelling and Storage

Lumentin® 44 powder for oral foam will be supplied in white sachets labelled according to EU-GMP, Annex 13. Ten sachets will be placed in a secondary package consisting of white unprinted cardboard. Lumentin® 44 powder for oral foam should be stored at room temperature (below 25°C) in a restricted area, accessible to authorised personnel only.

9.4 Drug Accountability

The Investigator is responsible for maintaining accurate investigational product accountability records throughout the trial.

Each dispensing of investigational product will be documented in the drug accountability log and the CRF.

All unused investigational product (Lumentin® 44 powder for oral foam) will be returned to Lument AB at the end of the trial.

9.5 Lumentin® 44 Exposure and Compliance

All Lumentin® 44 containers will be weighed before they are dispensed to the subject and again when returned by the subject and these weights (in gram) will be recorded in the CRF.

The exact volume of the Lumentin® 44 foam in the drinking container will be determined prior to dispensing it to the subjects but it will be at least 1.1 L. The weight of the contrast agent will be measured prior to dispensing and any remaining contrast agent will be weighed after intake. Volumes will be noted in the CRF Drug accountability will be carried out at regular intervals, as specified in the monitoring plan.

Drug exposure will be estimated based on the weight of ingested contrast agent and the weight of the subject.

Data from this trial will be used to the extent possible for providing future advice as of how much Lumentin® 44 should be used to obtain MRE scans with good diagnostic readability.

10 PROHIBITED PREVIOUS AND CONCOMITANT MEDICATION

10.1 Concomitant Medication

Any medication the subject takes other than the investigational product (prescribed and over-the-counter-drugs) is considered a concomitant medication. All concomitant medications must be recorded in the CRF. The following information must be recorded in the CRF for each concomitant medication: generic name, route of administration, start date, stop date, dosage, and indication. Any changes in the dosage or regimen of a concomitant treatment must be recorded in the CRF.

At visit 1, subjects will be asked what medications they have taken during the last 2 weeks before visit 1. Concomitant medications will be recorded at each visit and during telephone interviews, if applicable.

All subjects will receive:

1. An intravenous injection of Buscopan 40 mg. The dose given and batch number of Buscopan 40 mg will be noted in the CRF
2. An intravenous injection of the Gd contrast agent (Clariscan®, 0.5M) during the MRE-examination at a dose of 0.1 mmol/kg b.w. The volume given is typically 10 – 20 ml. The dose given and batch number of the Clariscan® 0.5M will be noted in the CRF.

10.2 Permitted/Prohibited Medicines

All use of medication taken by any route will be prohibited during 4 hours before taking the contrast agents and one hour post the intake. Thereafter only contraceptives and occasional painkillers are allowed.

10.3 Permitted/Prohibited Procedures

HVs shall not undergo more than normal physical living during the first 24h of the study, meaning that training and hard physical exercise are not allowed.

10.4 Precautions/overdose

Risks associated with intake of oral contrast agents include dysphagia with aspiration and secondary pneumonia. Although this trial intends to enrol only healthy volunteers and subjects with acute problems are excluded, a pre-emergency small bowel status might be aggravated to an established ileus by ingesting a large volume. Oral contrast agents should not be given to unconscious subjects, to those with swallowing disorders, or an acute abdomen problem.

Known sensitivity or allergy to contrast agent ingredients are exclusion criteria in clinical studies. However, unknown sensitivities or allergies might cause reactions that may need to be medically treated.

Intravenously administered Gd may cause allergic reaction of various severity from a mild rash to intensive care unit treatment. This is especially true for those with allergic reactions to a contrast agent earlier in life. Allergic reaction may be triggered in those with asthmatic bronchitis and treated with beta-blockers. Routines for handling these cases are well known to the staff which is regularly trained in dealing with emergency cases. Equipment for emergency care treatment is available at the clinic and the clinic is located in close proximity to the hospital emergency care department. Neither Buscopan nor Gd should be administered to patients with severe kidney failure.

11 VISIT SCHEDULE AND ASSESSMENT DESCRIPTION

11.1 Visit schedule

11.1.1 Pre-screening visit (Visit 1: Day -21 to -1)

Pre-screening assessments will include:

- Recording of subject information.
- Recording of past medical and surgical history.
- Recording of concurrent illness and treatments.
- Eligibility check with regards to inclusion criterion 1 and exclusion criteria 2, 3, 4, 5, 6, 7, 8, 12 and 13.

11.1.2 Screening visit (Visit 2: Day 0)

Screening assessments will include:

- Obtaining of written informed consent prior to any study specific procedure (including screening procedures) being performed.
- Recording of subject information and demographics including, date of birth, sex, height and weight
- Recording of past medical and surgical history.
- Recording of concurrent illness and treatments.
- Inclusion/ exclusion criteria.
- Performing a physical examination.
- Females will be asked to undertake a urine pregnancy test
- Obtaining a creatinine blood sample

11.1.3 MRE examination visit (Visit 3: Day 14)

During this visit the MRE examination will be performed, including the following assessments:

- Recording of concomitant treatments
- Recording of AEs
- Placement of the IV antecubital cannula
- Dispensing of Lumentin® 44

- MRE examination
 - Administration of Gd contrast
 - Administration of Buscopan®
- Evaluation of extension and distension of bowel filling agents
- Blood sampling for electrolyte assessment (pre-, 1, 2, 4, 6, 8h)
- Recording of compliance

11.1.4 Blood sampling visit (Visit 4: Day 15)

During this visit the following assessment will be performed:

- Recording of concomitant treatments
- Recording of AEs
- Blood sampling for electrolyte assessment (24h)

11.1.5 F-U and early termination visit (Visit5: Visit 2±2 days)

During this visit the following assessment will be performed:

- Recording of concomitant treatments
- Recording of AEs

11.2 Assessment descriptions

11.2.1 Subject Demography

Subject demography consists of date of birth, sex, height and weight.

11.2.2 Medical History

For the documentation of the medical history, any previous and concomitant diseases within the last 2 years before screening will be documented in the CRF.

The medical history will be obtained by asking the subject and by inspecting his/her medical records if available.

For statistical analysis, all previous and concomitant diseases will be coded with Medical Dictionary for Regulatory Activities (MedDRA), the version of which will be provided in the trial report.

11.2.3 Pregnancy Test

In women of childbearing potential, urine pregnancy test will be performed at screening.

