Statistical analyses	
All subjects who have completed the trial will be included in the statistical evaluation.
 
No statistical tests will be conducted. Confidence intervals may be constructed and will then be 2-sided and of 95% confidence.
 
Continuous data will be summarised using descriptive statistics (N, mean, median, standard deviation, minimum and maximum). Categorical data will be summarised by frequency tables (numbers and percentages).
 
Unless otherwise stated, all analyses will be done on observed cases without any substitution of missing values.

Schedule of Assessments

Visit/Contact	1	2	3	4	5
	Pre-screening	Screening	MRE examination	Blood sampling	F-U ⁽¹⁾ and early termination
Day	-21 to -1	0	14	15	Visit 2 +2 days
Visit window (days)			+/- 7 days	-	+ 2
Subject information	X	X			
In/exclusion criteria	(X) ⁽²⁾	X			
Informed consent		X			
Physical examination		X			
Pregnancy test ⁽³⁾		X			
Creatinine blood sample		X			
Subject demographics (incl. height and weight)		X			
Concomitant treatment	X	X	X	X	X
Concomitant illnesses	X	X			
Medical history	X	X			
Adverse event(s) recording			X ⁽⁴⁾	X	X
Placement of IV antecubital cannula			X ⁽⁵⁾		

Visit/Contact	1	2	3	4	5
	Pre-screening	Screening	MRE examination	Blood sampling	F-U ⁽¹⁾ and early termination
Day	-21 to -1	0	14	15	Visit 2 +2 days
Visit window (days)			+/- 7 days	-	+ 2
MRE Scan			X		
Dispensing of Lumentin® 44			X		
Administration of Gd contrast (6)			X		
Administration of Buscopan® (6)			X		
Evaluation of extension and distension of bowel filling agents			X		
Blood sampling			X ⁽⁵⁾ (pre-, 1, 2, 4, 6, 8h)	X (24h)	
Compliance			X		

- 1) Subjects will be contacted by telephone two to four working days post MRE assessment.
- 2) Only some of the criteria will be checked including, inclusion criterion 1 and exclusion criteria 2, 3, 4, 5, 6, 7, 8, 12 and 13.
- 3) Urine pregnancy test of all females who are not surgically sterile (hysterectomy or tubal ligation) or postmenopausal (i.e., experienced 12 consecutive months without menstruation).
- 4) Telephone interviews will be conducted 2 days after MRE assessment to investigate if any AEs occurred during the first days after the imaging procedure
- 5) An IV antecubital cannula will be placed for pre-blood samples and used during the first 8h including administration of gadolinium during the MRE procedure. Thereafter it will be discarded. Blood sampling on the following day (24h time point) will be drawn without a cannula.

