7 OVERALL DESIGN AND PLAN OF THE TRIAL

7.1 Trial Overview

This is an uncontrolled, single centre phase II trial. Enrolled HVs (n=10) will undergo Gd-enhanced MRE after oral intake of Lumentin® 44.

Interested HVs will be identified primarily among medical students at the medical hospitals at Malmö and Lund. Posters will be placed at the departments and invitation letters will be handed out.

The HVs interested in participating will be invited to attend a pre-screening visit where their suitability based on age and health status will be assessed. Fifteen HVs who fulfil the pre-screening criteria and are interested in participating will be asked to attend a screening visit at the clinic and if eligible for the trial they will then visit the clinic for the MRE assessment within 1-2 weeks.

Only the initial 10 of the eligible HVs will be asked to come for the MRE examination and the remaining eligible subjects will be asked to stand by in case any of the 10 subjects are unable to come or cannot undergo the examination.

HVs will be asked to fast for 6 hours prior to the examination on the day of the MRE examination. Small amount of clear liquid is allowed up to 2 decilitres. Prior to MRE, Lumentin® 44 will be provided to them in volumes of up to 1,500 mL and at least 1,100 mL of Lumentin® 44 must be drunk. The subjects will be asked to drink the solutions of oral contrast agent within 45 minutes to 1 hour.

Subjects not able to drink at least 1.1 L of Lumentin® 44 will be withdrawn from the trial.

Prior to the intake of Lumentin® 44, an IV antecubital cannula will be placed and used for blood sampling and administration of gadolinium (Gd) contrast agent during the MRE assessment.

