8.1 Inclusion Criteria

Subjects will be entered into this trial only if they meet all the following criteria:

1. Healthy volunteers of either gender at least 18 years at the time of signing the informed consent.
2. Females must either present a negative pregnancy test or be surgically sterile (hysterectomy or tubal ligation) or postmenopausal (i.e., experienced 12 consecutive months without menstruation).
3. Following verbal and written information about the trial, the subject must provide signed and dated informed consent before any trial related activity is carried out.

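### The only pregnancy test is at screening, a week or more before exposure, and the passages conflict on which women must take it

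*Combined protocol and SAP*

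**What the plan says.** **When the test is done.** Section 11.2.3 states: "In women of childbearing potential, urine pregnancy test will be performed at screening". Section 11.1.2 is headed "Screening visit (Visit 2: Day 0") and lists the urine test. The Schedule of Assessments ticks the test, and the full check of inclusion and exclusion criteria, at Visit 2 and not at Visit 3.

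**When exposure occurs.** Section 11.1.3 is headed "MRE examination visit (Visit 3: Day 14"), and the schedule gives this visit a window of 7 days either side. The section opens with "During this visit the MRE examination will be performed, including the following assessments". Its list includes dispensing Lumentin 44, giving gadolinium and Buscopan, and the scan. It includes neither a pregnancy test nor an eligibility check. Section 7.1 describes the interval differently: "if eligible for the trial they will then visit the clinic for the MRE assessment within 1-2 weeks".

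**Who is tested.** The synopsis (Assessments) and section 11.1.2 apply the test to females and state no exemption. Section 11.2.3 limits it to women of childbearing potential, a term the protocol does not define. Schedule footnote 3 reads: "Urine pregnancy test of all females who are not surgically sterile (hysterectomy or tubal ligation) or postmenopausal". Inclusion criterion 2 (section 8.1) can be met in three ways: a negative test, surgical sterility, or being "postmenopausal (i.e., experienced 12 consecutive months without menstruation"). No age limit is given, and other causes of absent periods are not ruled out.

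**Contraception.** It appears only as a permitted medicine in section 10.2: "Thereafter only contraceptives and occasional painkillers are allowed". None of the 3 inclusion or 13 exclusion criteria requires it, and none names pregnancy as an exclusion.

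**The concern.** Criterion 2 is there to keep pregnant volunteers out of the trial, and section 12.2 has pregnancies reported and followed, so the sponsor evidently treats the event as important. A negative result on Day 0 describes Day 0. The exposures come at a later visit, and nothing planned in between would reveal a change.

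The volunteers are expected to be mainly young (section 7.3.2) and are recruited largely among medical students (section 7.1). Section 5.4 expects no direct benefit for them, which leaves little reason to accept an avoidable gap.

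The definition of postmenopausal adds a smaller difficulty. Read literally, it covers a young woman whose contraceptive has stopped her periods for a year. Some passages would test her and one would not, so the site cannot tell from the protocol what to do.

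**Working it through.** No sample-size or power calculation is involved. The check is date arithmetic followed by a comparison of passages.

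**Inputs**
- Test: Day 0 (section 11.1.2, section 11.2.3, schedule).
- Exposure visit: Day 14, window 7 days either side (schedule).
- Narrative interval from screening to MRE: 1 to 2 weeks (synopsis, section 7.1).
- Screening to follow-up: up to 17 days (section 16.4).
- Follow-up contact: 2 to 4 days after the MRE (section 11.2.5). Schedule footnote 1 says working days, which can only shorten the last interval in the table.

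**Interval from test to exposure**

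| Source | Calculation | Interval |
|---|---|---|
| Schedule | 14 − 7 to 14 + 7 | 7 to 21 days |
| Synopsis and section 7.1 | 1 × 7 to 2 × 7 | 7 to 14 days |
| Section 16.4 with 11.2.5 | 17 − 4 to 17 − 2 | at most 13 to 15 days |

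The sources do not agree. By the schedule, screening to follow-up could last from 7 + 2 = 9 to 21 + 4 = 25 days, and 25 exceeds the stated 17. Both sources that give a minimum put it at 7 days. Section 16.4 gives only a maximum. No passage places the test on the day of exposure.

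**What covers the interval**
1. Visit 3 has no test (section 11.1.3, schedule).
2. The row for inclusion and exclusion criteria is not ticked at Visit 3.
3. No criterion requires contraception (sections 8.1 and 8.2).
4. Section 8.3.2 withdraws subjects who violate eligibility and allows withdrawal at the investigator's discretion. Both depend on the pregnancy being known.
5. The reporting period in section 12.2 runs from the start of intake to follow-up. It therefore acts after exposure, and neither the Visit 5 list nor the schedule has a pregnancy test at follow-up.

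**Is a woman with a year of contraceptive-related amenorrhoea tested?**

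| Passage | Reading |
|---|---|
| Synopsis, Assessments | Yes |
| Section 11.1.2 | Yes |
| Section 11.2.3 | Probably yes, but the key term is undefined |
| Schedule footnote 3 | No, read literally |
| Inclusion criterion 2 | Accepted without a negative test, read literally |

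**Number affected.** Ten subjects are exposed, plus replacements from five on standby, so the ceiling is 10 + 5 = 15. Both sexes are eligible and no split is given, so the number of women is unknown and will probably be lower.

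**The case against.** The strongest reply is that the protocol does test before dosing. Contraceptive use would be known from the concomitant-medication record at Visits 1 to 3, the investigator would be unlikely to class a young contraceptive user as postmenopausal, and section 8.3.2 leaves room for discretion. With about ten exposed subjects and a short interval, few if any pregnancies would be expected.

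Much of this stands, and it rules out several stronger readings that a reader might infer:

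- **That a young contraceptive user without periods is never tested.** The documents do not support this. The synopsis and section 11.1.2 test females without exemption, and section 11.2.3 would ordinarily cover her. Only footnote 3 exempts her, and only criterion 2 lets her in without a negative result. This is a conflict between passages rather than a settled exemption.
- **That the gap is simply 21 days at its longest.** That limit comes from the schedule alone. Section 7.1 and section 16.4 both imply less.
- **That nothing detects a pregnancy before dosing.** The Day 0 test does, for pregnancies already detectable then.

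The reply does not answer the timing point. Medication records and discretion do not reveal a pregnancy that nobody knows about, and every reading that gives a minimum leaves at least 7 days between test and exposure.

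**Conclusion.** The point holds on timing. Followed exactly, criterion 2 establishes a negative test at screening but not the absence of pregnancy at exposure. The uncovered interval is at least 7 days; its upper end is between about 13 and 21 days, depending on which passage governs. Conceptions too recent to show on Day 0 add to this.

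On who is tested, the finding is that the passages contradict one another. The literal amenorrhoea route through criterion 2 and footnote 3 is real but secondary, because it also needs the investigator to apply the definition against its evident sense.

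The conclusion assumes that the schedule and section 11.1.3 list all planned Visit 3 procedures. It concerns a gap in the criteria. The documents give no conception rate and no fetal-risk figure for any of the exposures, so neither the probability nor the harm can be sized from them. The change is worth making because it is cheap and serves subject safety. It does not affect the endpoints or the analysis.

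**What to change.** 1. Perform the urine pregnancy test at Visit 3 before Lumentin 44 is dispensed, either moved from Visit 2 or repeated after it. Show it in the schedule and in sections 11.1.3 and 11.2.3, and word criterion 2 so that it refers to that result.
2. Reconcile the synopsis, section 11.1.2, section 11.2.3, footnote 3 and criterion 2 on who must be tested. The agreed wording should not exempt a woman with contraceptive-related amenorrhoea by accident. The sponsor should settle the definition.
3. Reconcile the interval from screening to MRE across the schedule, the synopsis, section 7.1 and section 16.4.

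**Cost.** Up to about ten dipsticks plus any for replacements, a few minutes at a visit that already has a pre-dose blood sample, one schedule tick and some redrafting. There is a small chance of losing a scan slot, which a standby subject would fill.

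**What remains.** A urine test on the day may still miss a very recent conception, so the gap is reduced and not eliminated.
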